Appendix 2 – Diabetic Foot Ulcer Scale – Short	
	Quality Control and Quality Assurance. Training

Celliant Clinical Trial Protocol
PI: [name]
Protocol #: HGX2020-01

Primary Study Contacts

UT Southwestern Medical Center, Department of Plastic Surgery

Principal Investigator	[name]
email	[contact]
[contact]

Parkland Hospital, Department of Plastic Surgery

Principal Investigator	[name]
email	[contact]
[contact]

Executive Summary

Title of Study Study to Evaluate Celliant Diabetic Medical Socks to Increase Tissue Oxygenation

and Incidence of Complete Wound Closure in Diabetic Foot Wounds

Protocol Number HGX2020-01

Study Purpose The purpose of this study is to demonstrate that the use of Celliant Socks

increases tissue oxygenation (via oxygen saturation, StO₂) and incidence of wound closure in subjects with diabetic foot ulcers. This study will use hyperspectral imaging and wound assessment to measure these outcomes.

Study Design This study is a prospective, multicenter, double-blind, 1:1 randomized clinical trial.

Enrollment The study will enroll 254 evaluable subjects total, 127 per arm to meet the Primary

Endpoint. Enrollment may continue up to twenty-five hundred (2500) evaluable subjects total to meet the Key Secondary Endpoint of complete wound closure.

Investigational UT Southwestern, Department of Plastic Surgery Sites Parkland Hospital, Department of Plastic Surgery

Study Duration Up to 28 weeks (including run-in and followup phase)

Efficacy EndpointsPrimary Endpoint: To compare the percent change from baseline in tissue oxygenation in Celliant and Control treated groups 12 weeks post initial application,

as measured by hyperspectral imaging.

Key Secondary Endpoint: To compare the incidence of complete wound closure of Celliant and Control treated groups 12 weeks post initial application.

Other Secondary Endpoints:

 Change in pain assessment as reported using the Visual Analog Scale (VAS)

- 2. 3-month follow-up to assess wound closure and reoccurrence
- 3. Accelerated wound closure as measured by changes in wound area, depth and volume.
- 4. Assessment of Compliance
- 5. Outcomes of Diabetic Foot Ulcer Scale Short Form
- 6. Study related AE/SAEs

Safety Endpoints The incidence of events reported

Study Groups

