- 5. Perform debridement if indicated. Debridement is to be performed using curette, scissors, scalpel, or forceps.
- 6. Collect 4 tissue specimens. Two in RNA later and two in DNA/RNA shield.
- 7. Perform standardized photography and measurement of the study wound (eKare or available camera with ruler). Assess the post-debridement ulcer area (cm²), perimeter (cm), and greatest depth (cm) using the inSight device (eKare, Fairfax, VA). These values are the baseline measurements for assessing accelerated wound closure at the two-week run-in visit.
- 8. Perform baseline SPP (note this procedure can be performed at any visit from baseline up to therapy initiation but before therapy is started).
- 9. Perform baseline tcpO2 (note this procedure does not need to be performed at baseline visit and can be performed at any visit through Run-In week 2/Therapy initiation visit).
- 10. Perform baseline hyperspectral imaging assessment on the dorsal and plantar aspects of the foot.
- 11. Perform neuropathy and pain assessment.
- 12. Obtain results from SOC hematology, blood chemistry, etc. that were not covered in inclusion/exclusion studies.
- 13. Subjects who do not meet eligibility and fail to qualify to enter the Run-in will be deemed Screen failures and discharged, noting the reasons for disqualification.
- 14. Collect all relevant concomitant medication (antibiotics, antifungals and other antiinfective therapies)
- 15. Wounds will be dressed SOC and offloaded per physician discretion.
- 16. Subjects who qualify to enter the run-in will be instructed to refrain from using excluded medications and return to the office for Run-in Visit 2 within 7 (±4) days.

Run-In Procedures/Therapy Initiation

Week 1 Run-in:

- 1. Assess target ulcer.
- 2. Perform debridement if indicated. Debridement is to be performed using a curette, scissors, scalpel, or forceps.
- 3. Perform standardized photography of the study wound.
- 4. Assess the post-debridement ulcer area (cm²), perimeter (cm), and greatest depth (cm) using the inSight device.
- 5. If wound size (ulcer area) increases/decreases by 30% or more, patient will be deemed a screen failure and removed from the study.
- 6. If wound size (ulcer area) decreases by less than 30%, patient wound will be treated with standard of care and return for run-in Week 2 Run-In within 7 (±4) days.

- 8. Perform pain assessment.
- 9. Collect all relevant concomitant medication (antibiotics, antifungals and other antiinfective therapies)

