7. Perform hyperspectral imaging assessment on the dorsal and plantar aspects of the foot.

10. Wounds will be dressed SOC and offloaded per physician discretion.

Week 2 Run-in/Therapy Initiation:

- 1. Assess target ulcer
- 2. Perform debridement if indicated. Debridement is to be performed using curette, scissors, scalpel, or forceps.
- 3. Perform standardized photography of the study wound.
- 4. Assess the post-debridement ulcer area (cm²), perimeter (cm), and greatest depth (cm) using the inSight device.
- 5. If wound size (ulcer area) increases/decreases by 30% or more, patient will be deemed a screen failure and removed from the study.
- 6. If wound size (ulcer area) increases/decreases by less than 30%, patient wound will enter the study and randomized to either the Celliant Active or Control treatment arm.
- 7. Perform hyperspectral imaging of the dorsal and plantar aspects of the foot
- 8. Perform pain assessment.
- 9. Collect all relevant concomitant medication
- 10. Wound will be dressed with SOC and either Celliant Active or Control Sock applied.
- 11. Wound will be offloaded.
- 12. Provide subject with any additional medical socks needed until the next visit. Instruct the subject to change the socks if they become wet, soiled, or bloody and under any conditions dictated by PI instructions.

Therapy/Treatment Phase

Study Visit 1-11:

- 1. Document study compliance information from the subject
 - a. Amount of time the sock was worn throughout the week
 - b. Was it worn during the day/night?
 - c. When/why the sock was changed.
 - d. Has the sock been on in the 3 hours leading up to the appointment?
- 2. Remove sock and dressing and immediately perform hyperspectral imaging of the dorsal and plantar aspects of the foot if wound is active or closed.
- 3. Assess target ulcer (if wound has closed, document as such, perform steps 7 and 8 and

- skip to Study Visit Wound Closed).
- 4. Debridement is to be performed, if indicated, using curette, scissors, scalpel, or forceps. If debridement is necessary at weekly visits, all therapy must be removed and replaced post-debridement.
- 5. Collect 4 tissue specimens at week 3 and at week 6. Two in RNA later and two in DNA/RNA shield.
- 6. Perform standardized photography of the study wound.
- 7. Assess the ulcer area (cm²), perimeter (cm), and greatest depth (cm) using the inSight device if the wound is deemed closed by the physician, skip to EOS visit.

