- 13. Administer DFS-SF
- 14. Collect all relevant concomitant medication
- 15. Redress the wound per physician-directed standard of care.

Study Visit Follow up

- 1. If the subject's wound closes within the 12-week treatment window, they will enter the follow up phase of the study.
- 2. At 3 months post closure, wound evaluation will be performed as outlined below. This follow-up visit will be in person. In the event that an in-person visit is not possible, a telehealth visit may be performed and documented as such.
 - a. Assess the study wound to determine that it remained closed
 - b. If the study wound has reoccurred
 - i. record the date of reoccurrence
 - ii. measure the size of dehiscence or re-ulceration
 - iii. exit the subject from the follow up phase
 - c. Assess the study foot for new sites of ulceration
 - i. record the date of reoccurrence
 - ii. measure the size of dehiscence or re-ulceration
 - iii. exit the subject from the follow up phase

Detailed Study Operations

Medical Status/History

• The New York Heart Association (NYHA) Functional Classification System: This system will be used to classify stage of heart failure. The New York Heart Association (NYHA) functional classification system is used to classify the stage of heart failure from Class I to IV (as shown in the table below). This system relates symptoms to everyday activities and the patient's quality of life.

Class	Patient Symptoms
Class I (Mild)	No limitation of physical activity. Ordinary physical activity does not cause undue fatigue, palpitation, or dyspnea (shortness of breath).
Class II (Mild)	Slight limitation of physical activity. Comfortable at rest, but ordinary physical activity results in fatigue, palpitation, or dyspnea.
Class III (Moderate)	Marked limitation of physical activity. Comfortable at rest, but less than ordinary activity causes fatigue, palpitation, or dyspnea.
Class IV (Severe	Unable to carry out any physical activity without discomfort. Symptoms of cardiac insufficiency at rest. If any physical activity is undertaken, discomfort is increased.

- Body Mass Index (BMI): BMI is calculated as the ratio of body weight in kilograms (kg) to height in meters squared (m²).
- Medical History: The following information will be collected from each subject
 - previous ulcer history
 - amputation history
 - lower extremity bypass
 - lower extremity angioplasty
 - coronary artery bypass surgery
 - cardiac angioplasty
 - arthritis
 - liver disease

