The table below shows the schedule of planned events for each subject in this study.

Weekly Visits (±4 days)

	vocaty violo (± radyo)						
	SC	BL/-2	-1	BL/0	1-11	*EOS	FUP @3mo
Informed Consent	Х						
Inclusion/Exclusion	Х						
Randomization				Х			
Medical History, Social, Demographics, PE, Vitals		Х					
Lab Values		X					
Vascular - SPP		Х			X**	Х	
Vascular – tcpO2		Х			X**	Х	
Vascular - HSI		Х	Х	Х	Х	Х	
Monofilament, VPT		Х					
Wound Assessment, Debridement		Х	Х	Х	Х	Х	Х
Tissue Collection (4 pieces)#		Х			X##	Х	
Wound Photography and Measurements		Х	Х	Х	Х	Х	Х
Pain Assessment		Х		Х	Х	Х	
Sock Application				Х	Х		
Offloading				Х	Х		
Adverse Events			Х	Х	Х	Х	Х
Concomitant Medication		Х	Х	Х	Х	Х	
DFS-SF						Х	
Subject Stipend			Х	Х	Х	Х	Х
			·		•		

^{*}if subject is deemed closed at week 12, subject will be observed at week 14 and will enter FUP phase

Trial Monitoring

Monitoring visits will be conducted by representatives of Hologenix according to the U.S. CFR Title 21 Parts 50, 56, and 812 and ICH Guidelines for GCP (E6). By signing this protocol, the Investigator grants permission to the Hologenix contact and appropriate regulatory authorities to conduct on-site monitoring and/or auditing of all appropriate study documentation.

Clinical monitors, qualified by training and experience, will be responsible for monitoring and

^{**}Visit 4 only, 5 or 6 if visit 4 is missed

[#]Two for RNA later and two for DNA/RNA shield

^{##} Weeks 3 and 6

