Prior to the database lock for the final primary endpoint analysis at 254 evaluable subjects, and again at any subsequent lock as dictated by the adaptive design for subjects evaluated after the final primary lock, an evaluability meeting will be held. The goal of the evaluability meeting is to identify the disposition of study subjects with respect to the predefined study populations.

Subject Demographic and Baseline Characteristics

Demographic and baseline characteristics of enrolled subjects will be summarized. The factors will include (but are not limited to): Age, sex, race, BMI (kg/m²), baseline Diabetic and Foot Ulcer Scale-Short Form (DFS-SF). Medical history, PE, and vitals will be provided in a listing.

Additional Efficacy Analyses including Subgroup Analyses

Secondary Endpoints: To compare the incidence of the below between Celliant and Control treated groups:

- 1. For subjects whose wound closes within the 12-week period, wound evaluation at 3 months following complete wound closes for the following parameters
 - a. Incidence of wound dehiscence/reoccurrence
 - b. Size of reoccurrence
- 2. Accelerated wound closure as measured by changes in wound area, depth and volume.
- 3. Assessment of Compliance
- 4. Change in pain assessment as reported using VAS pain scale
- 5. Outcomes of Patient Reported Outcomes
- 6. Study related AE/SAEs

Additional, ad hoc exploratory analyses may also be conducted for efficacy endpoints.

Safety Endpoints and Analyses

An overview of events, to include total numbers of events, and total number of subjects will be tabulated and presented for all AEs, SAEs, procedure-related AEs by treatment type. Device specific risks such as "skin and subcutaneous tissue reaction/allergy" and "mild pain or discomfort" will also be tabulated in a separate summary table.

Additional, ad hoc exploratory analyses may also be conducted for safety endpoints.

Poolability

Pooling of outcome data from different clinical study sites will be performed by evaluating the homogeneity of the primary efficacy endpoint across sites. If the treatment by site interaction is $p \ge 0.2$, then homogeneity will be considered to be demonstrated across sites. If p<0.2, then site level variable will remain in the analysis models.

Handling of Missing Data

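### Section 4 plans a summary of baseline DFS-SF, but the questionnaire is given only at the end-of-study visit, so that row will be empty and the DFS-SF endpoint can be compared only as an EOS score without baseline adjustment

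*Combined protocol and SAP*

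**What the plan says.** In Section 4, under Subject Demographic and Baseline Characteristics, the plan states: "Demographic and baseline characteristics of enrolled subjects will be summarized". The factors it then names include "baseline Diabetic and Foot Ulcer Scale-Short Form (DFS-SF").

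The DFS-SF is also an endpoint. The Executive Summary lists "Outcomes of Diabetic Foot Ulcer Scale Short Form" as other secondary endpoint 5. The secondary endpoint list in Section 4 has "Outcomes of Patient Reported Outcomes" in the same position. Neither entry defines a change from baseline.

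Collection is set out in Section 3. The visit list for Study Visit 12/EOS has, at step 13, "Administer DFS-SF". The Patient Reported Outcomes paragraph says that the instrument will be used but gives no time point. The Schedule of Events Table has a DFS-SF row with one mark, under EOS.

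**The concern.** The analysis text assumes a pre-treatment score that the visit procedures never produce. Sites that follow the visit lists will leave one row of the baseline table empty, and a pre-treatment score cannot be recovered once a subject has worn the sock.

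This also limits a listed secondary endpoint. With one post-randomisation score per subject, the arms can be compared on that score, but nobody can see whether they started level on foot-ulcer quality of life, and the baseline score cannot be used to remove between-subject variation. The gap recurs with every subject, in a trial that may run from 254 to 2500 evaluable subjects.

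**Working it through.** The documents give no power or sample-size figure for the DFS-SF, so there is no stated number to reproduce. The check is a trace of the instrument through the protocol, followed by a short illustration of the precision lost.

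**Trace of the DFS-SF**

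| Place in the protocol | DFS-SF present? |
|---|---|
| Screening | No |
| Baseline, steps 1–16 | No; step 11 is "Perform neuropathy and pain assessment" |
| Week 1 Run-in | No |
| Week 2 Run-in/Therapy Initiation, steps 1–12 | No; step 7 is "Perform hyperspectral imaging of the dorsal and plantar aspects of the foot", step 8 is pain |
| Study Visits 1–11 | No |
| Study Visit 12/EOS | Yes, step 13 |
| Study Visit Follow up | No |
| Schedule of Events Table | One mark, in the sixth of seven columns (EOS) |
| Patient Reported Outcomes paragraph | No time point given |

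The table introduces itself with "The table below shows the schedule of planned events for each subject in this study". Its columns run SC, BL/-2, -1, BL/0, 1-11, EOS, FUP. Counting cells puts the Randomization mark in column 4 (BL/0) and the DFS-SF mark in column 6 (EOS). The table and the visit lists agree, so the gap does not come from a table broken in the PDF conversion.

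Scheduled administrations per subject: 0 before randomisation, 0 at Visits 1–11, 1 at EOS, 0 at follow-up.

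**Precision lost (illustrative)**

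Let r be the correlation between baseline and EOS DFS-SF within arm. The documents give no value, so a range is assumed. Relative to comparing EOS scores alone, a linear model with baseline as covariate multiplies the variance of the arm difference by 1 − r². The equivalent sample-size multiple is 1/(1 − r²).

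| Assumed r | 1 − r² | Variance reduction | Equivalent sample-size multiple |
|---|---|---|---|
| 0.3 | 1 − 0.09 = 0.91 | 9% | 1/0.91 = 1.10 |
| 0.5 | 1 − 0.25 = 0.75 | 25% | 1/0.75 = 1.33 |
| 0.7 | 1 − 0.49 = 0.51 | 49% | 1/0.51 = 1.96 |

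**Burden of the questionnaire**

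The form in Appendix 2 has 5 + 5 + 5 + 10 + 4 = 29 items.

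**The case against.** The case for leaving the design alone is a fair one, and most of it stands.

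- **Baseline DFS-SF is used only descriptively.** It appears in a list of characteristics to be summarised. The mixed model for the primary endpoint and the logistic model for closure adjust for wound size and site, not for DFS-SF. A reader might infer that a planned inferential analysis fails; the documents do not support that.
- **No DFS-SF change score is planned.** The endpoint lists speak of change for pain and for wound dimensions but only of outcomes for the DFS-SF. A reader might infer that a promised change in quality of life cannot be delivered. No such promise is made. That change cannot be calculated is a consequence of the gap, not a second contradiction.
- **The EOS comparison does not need a baseline to be unbiased.** Randomisation provides for that. Balance can still be examined on related pre-treatment measures that are collected, such as VAS pain and wound size.
- **Variable EOS timing is a separate matter.** EOS falls at closure for early closers and at week 12 for the rest. A reader might take this as part of the same fault, but a pre-treatment questionnaire would not cure it.
- **The precision gain rests on an assumed correlation**, and the DFS-SF has no hypothesis, no power calculation and no place in the testing hierarchy.

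The contradiction between Section 4 and the visit schedule survives all of this. VAS pain, also reported by the patient, is collected before treatment, and Section 4 expects a DFS-SF baseline as well. Together these suggest an omission from the schedule more than a deliberate EOS-only design, though the documents do not settle which was meant.

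**Conclusion.** The point holds as an internal inconsistency of limited reach. One named row of the baseline table cannot be filled. One secondary endpoint outside the testing hierarchy loses precision and a check of balance on its own baseline. The first loss is certain if the visit lists are followed. The second depends on r: a variance reduction of 9% to 49% forgone for r between 0.3 and 0.7, a range chosen for illustration.

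It should not be read as showing that the DFS-SF comparison is invalid. The primary endpoint, the key secondary endpoint and VAS pain are untouched, and no stated power or alpha figure changes. It is still worth correcting now, because the remedy is cheap and the missing score cannot be collected later.

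**What to change.** **Preferred.** Add the DFS-SF to the Week 2 Run-in/Therapy Initiation list, after the wound-size check at step 5 and before randomisation at step 6, so that only subjects going on to randomisation complete it. Add a mark in the BL/0 column of the Schedule of Events Table. In Section 4, define the DFS-SF analysis as a comparison of EOS scores with baseline DFS-SF as a covariate.

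The cost is one extra 29-item questionnaire per subject at an existing visit, plus an amendment to the visit list and schedule. It needs no additional visit or invasive procedure. If any subjects were randomised before the amendment, Section 4 should also say how their missing baselines will be handled.

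**Alternative.** If EOS-only collection is intended, delete baseline DFS-SF from the list of baseline characteristics and state that the endpoint is a comparison of EOS scores only. This costs a text edit and removes the contradiction, but gives up the precision and the balance check.

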- Major immunodeficiency including HIV.
- Is pregnant or plans to become pregnant
- Is nursing or actively lactating

Celliant Clinical Trial Protocol
PI: [name]
Protocol #: HGX2020-01

 Developmental disability/significant psychological disorder that in the opinion of the investigator could impair the subject's ability to provide informed consent, participate in the study protocol or record study measures, including untreated schizophrenia, bipolar disorder and psychiatric hospitalization within the last 2 years.

 Active alcohol or substance abuse in the opinion of the investigator that could impair the subject's ability to provide informed consent, participate in the study protocol or record study materials

Withdrawal of Subjects

Subjects may withdraw from the study at any time at their own request, or they may be withdrawn at any time at the discretion of the PI for safety, behavioral, or administrative reasons. If a subject does not return for a scheduled visit, every effort should be made to contact the subject, per institutional protocol. In any circumstance, every effort should be made to document subject outcome. The Investigator should inquire about the reason for withdrawal, request that the subject return for a final visit, if applicable, and follow up with the subject regarding any unresolved AE's.

Any related SAE occurring within 14 days following subject discontinuation must be reported to Hologenix and be followed up until stabilization or resolution. If the Subject withdraws from the study, and also withdraws consent for disclosure of future information, no further study evaluations will be performed, and no additional data will be collected. The PI may retain and continue to use any data collected before such withdrawal of consent.

The Investigator may choose to withdraw their own participation or discontinue a Subject from study with or without their consent for any of the following:

- Adverse Events
- Non-compliance
- Safety
- Complications
- Unforeseen events

A patient who experiences the noted changes, relative to previous measures, in the following parameters will be terminated early from study participation

- An increase in ulcer size by 50% or more prior to debridement from previous visit.
- An increase in pain rating by 50% or more from previous visit.
- Presence of infection as determined by 2 more bacterial infection indicators that requires treatment outside the study scope

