Internal audits are done periodically to assure regulations, guidelines and protocols are adhered to appropriately. Patient binders are reviewed for proper informed consent process documentation, case report forms are compared to the source documents and reviewed for accuracy and an independent review of the inclusion and exclusion criteria using a checklist. Additionally, the use of an auditing and monitoring tool which includes sections on consent, HIPAA, on study/treatment, off treatment/off study and a general section. Weekly meetings occur to go over each study. If there are any issues that arise, they are brought up and discussed at the meeting.

4. Statistical Analyses

General Statistical Considerations

This study is a prospective, sham-controlled, subject and evaluator blinded, 1:1 randomized, multicenter clinical study. The duration of the study is up to four months for randomized subjects. Sample size may not be reduced less than the expected total enrollment of 254 evaluable subjects total but may increase up to a total of 2500 evaluable subjects. Sample size will increase based on actual attrition that is expected to be between 5 and 15%.

The purpose of this study is to evaluate safety and efficacy outcomes related to the Celliant Sock (CS). The p-value thresholds for determining statistical significance are 0.05 and 0.025 for 2- and 1-sided tests, respectively, unless otherwise specified.

Protocol #: HGX2020-01

Data will be presented using summary statistics. For example, continuous data may be displayed with the mean, median, minimum, maximum, and/or standard deviation, while categorical data may be displayed as proportions and counts.

Any changes to the analysis of the trial data will be documented either in a future protocol amendment or in the SAP.

Randomization

Randomization will be conducted in a 1:1 ratio of the Treatment Group (Celliant Sock, n=127) or to a sham Control Group (placebo sock, n=127). Randomization will be performed within randomly selected block sizes of 3 and 6 with equal probability of group assignment stratified by study center and wound size (greater than size of 4 cm²).

A Sponsor-designated independent statistical consultant will provide the randomization list. Sponsor personnel directly involved in the management, conduct, and reporting of the study will not have access to randomization assignments until the study is completed.

Analysis Population

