The primary population for the effectiveness analyses will be the intent-to-treat (ITT) population, which will include all randomized subjects regardless of whether the socks were ever worn. Subjects will be assessed to the group to which they were randomized, regardless of whether they were provided the wrong socks.

A secondary population for effectiveness analyses will be the (AT) population, including subjects that attempted to put on the sock for any amount of time. These subjects will be analyzed according to the type of socks (Celliant or Placebo) they received. This population is also the safety population, which is the population used for all safety analyses.

A third population is the modified full analysis set (mFAS), which consists of all subjects that report wearing the sock as directed for at least 10 days.

Sample Size Justification

Assuming a 2-sided alpha at 0.05, and a power of 0.85, the true mean difference at 12 weeks between groups in percent change in tissue oxygenation as measured by hyperspectral imaging is estimated to be 8.2 with a standard deviation of 21.7. At a 1:1 allocation of experimental to control subjects, a total of 254 evaluable subjects are required. The sample size will increase to account for attrition at Week 12.

Analyzing the sample size for the key secondary endpoint of incidence of complete wound closure suggests a much large trial is need. Specifically, at 2500 evaluable total subjects, there would be approximately a power of 0.85 to detect a difference in incidence of complete wound closure at 12 weeks if the expected incidence of complete wound closure was 25% in the experimental group, and 20% in the control group, an absolute difference of 5% between the experimental group and the control group.

Primary Efficacy Analyses

The primary efficacy endpoint is an inferential test of whether the Treatment Group (Celliant[®] Diabetic Medical Sock) percent change in tissue oxygenation (via oxygen saturation, S_tO₂) compared to the Control Group (placebo sock) at 12 weeks is superior.

Effectiveness variables will be analyzed relative to the mean of the Weekly visit 0 and -1 tissue oxygenation measurements. For purposes of statistical analysis, this mean will be referred to as the baseline.

The hypotheses are:

```
H0: %ChgPerfCelliant ≤ %ChgPerfPlacebo
Ha: %ChgPerfCelliant > %ChgPerfPlacebo
```

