A list of subjects who were withdrawn from the study and their associated reasons for withdrawal will be provided. A list of subjects lost to follow-up will also be provided. If the missingness of tissue oxygenation data or total wound closure data at 12 weeks is missing in more than 7.5% of subjects, multiple imputation will be performed, creating n=5 fully imputed complete datasets for the primary and key secondary endpoint, to be evaluated combined through a t-test, after the

Protocol #: HGX2020-01

predefined analyses are provided for each imputed data set. A non-imputed analysis will also be provided.

5. Data Management

Standardized CRFs will be created at all participating sites. Investigators are responsible for the accurate completion and timely submission of the data collected during the trial. All data from the trial will be entered from the CRFs into a central database. Incoming data will be frequently reviewed to identify inconsistent or missing data and any adverse events. Any data issues are to be promptly addressed with the investigator Quality assurance procedures will be established to ensure that complete, accurate and timely data are submitted, that protocol requirements are followed, and that complications, adverse events and adverse device effects are correctly reported and investigated, as appropriate. Investigators are to maintain all source documents as required by the protocol, including laboratory results, supporting medical records, and signed Informed Consent Forms. The source documents will be used during the regular monitoring visits to verify information from the database against data contained on the completed CRFs.

6. Deviations from the Investigational Plan

Any deviations from the study protocol will be documented as Protocol Deviations in the Source Documentation.

7. Device Accountability

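### Imputing only above 7.5% missing, with five unseeded datasets, leaves terminated subjects' closure status undefined and lets the seed decide borderline results

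*Combined protocol and SAP*

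**What the plan says.** Section 4, Handling of Missing Data, makes imputation conditional. It is done if either 12-week tissue oxygenation or 12-week closure is missing in more than 7.5% of subjects. The method is "creating n=5 fully imputed complete datasets for the primary and key secondary endpoint", each analysed as planned and then combined through a t-test. The section adds: "A non-imputed analysis will also be provided". It gives no imputation model and no seed, and it does not say whether the imputed or the non-imputed result decides success.

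Other parts of the plan bear on this:

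- Section 4, Analysis Population: the primary population is ITT, "which will include all randomized subjects regardless of whether the socks were ever worn".
- Section 4, General Statistical Considerations: attrition is expected to be 5 to 15%.
- Section 4, Primary Efficacy Analyses: StO2 is analysed by MMRM.
- Section 4, Interim Analysis for the Key Secondary Endpoint: closure is analysed by a logistic model adjusted for the stratification variables.
- Section 2, Withdrawal of Subjects: subjects with listed changes, including ulcer growth of 50% or more, infection and osteomyelitis, "will be terminated early from study participation". Neither this section nor Section 4 says how they are scored for closure.

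**The concern.** A logistic model for a single 12-week outcome has nothing to use for a subject without that outcome. Below the trigger, such subjects leave the analysis unless a scoring rule keeps them in, and the plan has none. Several of the listed reasons for termination describe a wound that is getting worse, so the loss can be related to the outcome. Dropping those subjects removes probable failures and inflates the closure rate. If the arms lose them unequally, it also shifts the difference.

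Above the trigger the method changes. Because the trigger lies within the expected attrition, a few subjects can decide which method is used. Five imputations without a fixed seed then mean that the same data can give p-values on either side of the threshold.

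Closure drives the interim decisions on stopping and sample size, and it gates the test of VAS pain, so an open rule for closure carries through to both. The StO2 endpoint is less exposed, because an MMRM uses the visits that a subject did attend.

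**Working it through.** **1. The plan's own figures.** The inputs are in Section 4, Sample Size Justification: "Assuming a 2-sided alpha at 0.05, and a power of 0.85"; the StO2 difference "is estimated to be 8.2 with a standard deviation of 21.7"; 1:1 allocation.

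- StO2: n per arm = 2(1.960 + 1.036)² × 21.7² / 8.2² = 125.8 by the normal formula. The t-test version gives 126.7, so 127 per arm and 254 in total. This reproduces.
- Closure, 25% v 20% with 1250 per arm: power 0.85. This reproduces.

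The planned sizes are therefore sound on their own assumptions. The question is only how missing outcomes are treated.

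**2. The trigger in subjects.** 7.5% is about 19 of 254, 38 of 508 or 188 of 2500.

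**3. Closure below the trigger.** The assumptions are mine, since the documents give no loss by arm or by reason: true closure of 20% in both arms, loss of 10% (sock) v 5% (control), every leaver a non-closer, and 12-week StO2 also missing in no more than 7.5%. Overall loss is (10 + 5)/2 = 7.5%, which is not more than 7.5%, so nothing is imputed.

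- Observed rates: 0.20/0.90 = 22.2% and 0.20/0.95 = 21.1%. The false difference is 1.17 points, against a planned effect of 5.
- Standard error: SE = √[p₁(1−p₁)/n₁ + p₀(1−p₀)/n₀], with n₁ = 0.90 × N/2 and n₀ = 0.95 × N/2.
- One-sided error = 1 − Φ(1.960 − 0.0117/SE), a single nominal test at 0.025 that ignores the group-sequential boundary.

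| N randomised | SE | Shift in z | One-sided error | Loss reversed (5% v 10%) |
|---|---|---|---|---|
| 254 | 0.0538 | 0.218 | 0.041 | 0.015 |
| 508 | 0.0380 | 0.308 | 0.049 | 0.012 |
| 2500 | 0.0171 | 0.683 | 0.10 | 0.004 |

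Sensitivity to the split:

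- Equal loss of 7.5% moves both rates to 21.6%. The difference is unbiased and the error stays at 0.025.
- Loss of 9% v 6% gives 0.034, 0.038 and 0.061.
- Loss of 12% v 3% gives 0.058, 0.080 and 0.23.

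Scoring these leavers as not closed restores 20% v 20% and an error of 0.025.

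**4. Seed dependence above the trigger.** One borderline closure dataset was held fixed and imputed repeatedly within arm, without auxiliary variables, and pooled by Rubin's rules.

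- 254 subjects, 15% missing: the SD of z between seeds is about 0.2 with m = 5 and about 0.065 with m = 50. As a rough check, √(FMI/m) with FMI = 0.15 gives 0.17 and 0.055.
- N = 2500, 10% missing: the 95% range of one-sided p over seeds is 0.011 to 0.050 with m = 5, and 0.018 to 0.029 with m = 50.
- Relative efficiency of m = 5 is 1/(1 + 0.15/5) = 97%, so average power is hardly affected.

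**The case against.** **The no-imputation case may be narrow.** The trigger is an OR, so missing StO2 alone can switch imputation on for closure. Subjects who close early have their end-of-study visit at closure, and the Schedule of Events shows no hyperspectral imaging at follow-up. With planned closure of 20 to 25%, 12-week StO2 could exceed 7.5% missing unless the end-of-study image counts as week 12. The midpoint of expected attrition (10%) also exceeds the trigger. This stands: the error rates in step 3 apply only when both variables are at or below 7.5%.

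**Complete-case is an inference.** The plan does not use the term. A subject terminated with an open wound could be scored as not closed and never be missing, and Section 2 asks sites to make every effort to document the outcome. So a reader might infer an outright contradiction of ITT, but the text is silent on scoring, which is a gap.

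**Three stronger readings do not hold.**

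- Unequal terminations alone do not bias closure. Loss unrelated to outcome leaves 20% v 20%.
- Nothing shows that many leavers go because of wound growth or infection. Section 2 lists reasons without frequencies.
- The plan does not let anyone pick the method by result. The switch is prespecified and depends on the missingness rate. The wording also suggests, without stating it, that the imputed analysis leads.

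**Five imputations are not wrong in general.** Efficiency is high, clear results are unaffected, and weekly wound measurements used as auxiliaries would narrow the seed ranges. The t-test combination may well mean Rubin's rules.

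**Scoring every leaver as not closed has its own cost.** With 10% v 5% loss unrelated to healing, it gives 0.20 × 0.90 = 18% v 0.20 × 0.95 = 19%, a false −1.0 point. This stands and limits the fix.

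**Conclusion.** The concern holds in limited form. The plan does not say how terminated subjects count for closure, makes imputation depend on a threshold inside its own expected attrition, uses five datasets without a seed, and does not state which result is decisive.

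The bias needs three things together: no imputation, outcome-related loss, and a difference in that loss between arms. Under the assumed 10% v 5% split with all leavers non-closers, the false difference is 1.2 points. It runs in favour of the sock or against it, depending on which arm loses more. The split is an assumption and not a forecast. Seed dependence changes a conclusion only for results near 0.025, and the simulated spread assumes no auxiliary variables. The gap should be closed before unblinding.

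**What to change.** - Remove the 7.5% trigger.
- For closure, score as not closed those subjects who were terminated for wound deterioration, infection or osteomyelitis with the wound open. Do not extend this to every leaver in the main analysis.
- For other unknown closure status, use multiple imputation with the weekly wound measurements as auxiliaries, at least 50 imputations, a fixed seed and Rubin's rules.
- Name one decisive analysis per endpoint: the MMRM for StO2 and this ITT analysis for closure.
- Report complete-case closure, and closure with all missing scored as not closed, as sensitivity analyses.

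The cost is SAP wording, a little more analysis work and trivial computing time. Reported closure rates will be slightly lower than complete-case rates.
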